	
[REDACTED]
 
[REDACTED]
 
[REDACTED]
 
[REDACTED]
 
[REDACTED]
 
[REDACTED]
 
[REDACTED]
 
[REDACTED]
 
[REDACTED]
 
[REDACTED]
 
[REDACTED]
 
[REDACTED]
 
[REDACTED]
 
[REDACTED]
 
[REDACTED]
 
[REDACTED]
 
[REDACTED]
 
[REDACTED]
 
[REDACTED]
 
[REDACTED]
 
[REDACTED]
 
[REDACTED]
 
[REDACTED]
 
[REDACTED]
 
[REDACTED]
 
[REDACTED]

Study Objective:	
The purpose of the study is to assess the safety and device performance of the Edwards FORMA Tricuspid Transcatheter Repair System in patients with clinically significant, symptomatic, tricuspid regurgitation who are at high surgical risk for standard tricuspid repair/replacement.

Study Devices:	
The Edwards FORMA Tricuspid Transcatheter Repair System:
 
 • Edwards FORMA Tricuspid Spacer System, [REDACTED] • Edwards FORMA Tricuspid Introducer Sheath, [REDACTED] • Edwards FORMA Tricuspid Railing Delivery System, [REDACTED] • Edwards FORMA Tricuspid Retrieval System, [REDACTED]
Intended Use:	
The Edwards FORMA Tricuspid Transcatheter Repair System is intended for treatment of subjects with tricuspid regurgitation who are at high surgical risk for standard tricuspid repair/replacement due to operative risks, long recovery time, and/or significant co-morbidities.

Study Design:	
This is a multi-center (≤ 12), international, prospective, single arm, safety study. 78 subjects will be enrolled in the study. All enrolled study subjects will be assessed for clinical follow-up at the following intervals: 1 month, 6 months, 1 year and annually for 3 years post implant procedure.

Study Duration:	
[REDACTED]
 
[REDACTED]
 
[REDACTED]
 
[REDACTED]
 
[REDACTED]
 
[REDACTED]

Study Population:	Adult subjects with clinically significant, symptomatic, tricuspid regurgitation who are at high surgical risk for standard tricuspid repair or replacement as assessed by the Heart Team.
Enrollment Criteria (Inclusion):	
 1. Signed and dated EC approved study consent form prior to study related procedures 2. Eighteen years of age or older 3. Clinically significant, symptomatic (NYHA Functional Class II or greater), tricuspid regurgitation (Stage D per 2014 AHA/ACC guidelines) requiring tricuspid valve repair or replacement as assessed by the Heart Team 4. Functional tricuspid regurgitation (e.g., EROA \geq 0.4 cm² or equivalent guideline directed value) as the primary etiology 5. NYHA Functional Class II or greater or signs of persistent right heart failure, despite optimal medical therapy 6. Determined by the 'HEART Team' (a minimum of one Cardiologist, and one Cardiac Surgeon) to be at high surgical risk for tricuspid valve repair or replacement and the benefit-risk analysis supports utilization of the investigational device 7. Willing to attend study follow-up assessments for up to 3 years
Enrollment Criteria (Exclusion):	
 1. Tricuspid valve/right heart anatomy not suitable for the study device: 
 a. Native tricuspid annulus area $<$ 2.14 cm² (9 mm device), $<$ 2.63 cm² (12 mm device) or $<$ 3.27cm² (15 mm device) as measured by transthoracic echocardiography or computed tomography b. Sub-valvular structures/anatomy that would preclude from proper anchor or Spacer placement, positioning and retrieval c. Access pathway vessel diameter less than 7.1 mm (9, 12 and 15 mm devices) 2. Moderate or greater tricuspid valve stenosis 3. Untreated clinically significant coronary artery disease requiring immediate revascularization 4. Any therapeutic invasive cardiac procedure performed within 30 days of the scheduled implant procedure 5. Patients not already receiving dialysis with renal insufficiency (eGFR $<$ 25) per lab test \leq 48 hours prior to scheduled implant procedure 6. Myocardial infarction within 30 days of scheduled implant procedure 7. Hemodynamic instability within 30 days of scheduled implant procedure 8. Patient requiring surgery under general anesthesia for any reason within 30 days of scheduled implant procedure 9. Severe left ventricular dysfunction with ejection fraction $<$ 25% within 90 days of scheduled implant procedure

	
 10. Patients with pulmonary artery systolic pressure > 70 mmHg via transthoracic echocardiography or alternative standard modality (e.g., direct pressure measurement) within 90 days 11. Concomitant clinically significant valve (aortic, mitral, or pulmonic) disease requiring immediate (\pm 30 days of study procedure) repair or replacement 12. Active endocarditis or infection within 3 months of scheduled implant procedure 13. Cerebrovascular accident within 3 months of scheduled implant procedure 14. Non-cardiac disease limiting life expectancy to be less than 12 months at baseline evaluation 15. Documented history of bleeding diathesis, coagulopathy or gastrointestinal bleeding within 3 months of scheduled implant procedure 16. Evidence of right sided intracardiac mass, thrombus, or vegetation 17. Prior venous stent placed within the access route (e.g., sub-clavian vein) that could negatively react with device 18. Previously treated tricuspid valve which included implantation of a bioprosthetic valve or mechanical valve 19. Known hypersensitivity to cobalt chromium, nitinol or titanium 20. Known hypersensitivity to anticoagulation therapy or contrast agent, which cannot be adequately medicated 21. Patient is a current intravenous drug user 22. Female of child-bearing potential is pregnant or lactating 23. Patient is currently participating or has participated in another investigational drug or device clinical study within 30 days of study screening activity 24. Patient requires emergent/emergency treatment for tricuspid insufficiency 25. Patient is under guardianship
Primary Endpoint:	The primary endpoint for the study will assess the all-cause mortality of the as treated cohort at 30 days compared to a literature derived Performance Goal based on high-risk surgical outcomes for tricuspid repair/replacement.
Secondary Endpoints and Clinical Outcomes:	
The following secondary endpoints and clinical outcomes will also be assessed:
 
Technical Success (at exit from procedure room):
 
 • Alive, with • Successful access, delivery and removal of the delivery systems, and • Deployment and correct positioning of the intended device, and • No need for additional emergency surgery or re-intervention related to the device or access procedure

	
Device Success (at 1 month, 6 months & Annually):
 
 • Alive, with • Original intended device in place, and • No additional surgical or interventional procedures related to the device, and • TR reduction (assessment made by change in EROA) compared to baseline and TV gradient $\leq 5\text{mmHg}$ 
Procedural Success (at 1 month):
 
 • Device Success, and • None of the following device or procedure related SAEs: 
 • Life threatening bleeding • Major vascular or cardiac structural complications requiring intervention • Pericardial effusion requiring drainage or surgery (includes tamponade) • Stage 2 or 3 acute kidney injury (includes new dialysis). • Severe heart failure or hypotension requiring IV inotrope, ultrafiltration or mechanical circulatory support • Prolonged intubation > 48 hours 
Clinical Outcomes (at 1 month, 6 months & Annually)
 
 • Re-hospitalization rates for the underlying condition (heart failure) • Re-intervention rates for the underlying condition (tricuspid regurgitation) • Change in Tricuspid Regurgitation (assessment made by change in EROA) from baseline • Change in peripheral edema as assessed by subject weight loss (kilograms) from baseline • Change in NYHA Class from baseline • Change in 6 minute walk test distance (meters) from baseline • Change in Quality of Life as assessed by the SF-12 and KCCQ questionnaires from baseline

Study Committee:
	
Independent Data Monitoring Committee (DMC)
 
The DMC will consist of a minimum of 3 members, all members being physicians; one cardiothoracic surgeon, one interventional cardiologist and one cardiologist

Echocardiography Core Laboratory:
	
[REDACTED]
 
[REDACTED]
 
[REDACTED]
 
[REDACTED]

1 INTRODUCTION

1.1 CLINICAL BACKGROUND

1.1.1 DISEASE PROCESS

Tricuspid Regurgitation (TR), tricuspid insufficiency or tricuspid incompetence describes a condition in which blood flow through the tricuspid valve flows in the incorrect direction during part of the cardiac cycle. Normally, during diastole, the tricuspid valve opens as a result of atrial pressure from the right atrium, allowing blood to flow through the tricuspid valve, into the right ventricle. Diastole ends with atrial contraction and the tricuspid valve closing to prevent a reversal of blood flow. However, in patients with TR, the tricuspid valve is unable to form a tight seal at diastole end (when it should be closed), allowing blood to flow back into the right atrium.

[figure not shown]
Although TR often accompanies mitral or aortic valve disease, it is usually asymptomatic, traditionally considered less clinically significant, and left untreated. This scenario where the tricuspid valve is left untreated has resulted in the tricuspid valve being commonly referred to as the “forgotten” valve. While trace to mild levels of TR are commonly found in a large number of patients without clinical consequence, moderate and severe levels can have detrimental effects on a patient's quality of life [1]. Patients with severe TR usually present with signs or symptoms of right heart failure (HF), including peripheral edema and ascites [2].

1.1.2 ETIOLOGY

TR can have many underlying etiologies, but the majority of these can be divided into two major categories: degenerative and functional TR. Degenerative (primary, organic or structural) TR refers to regurgitation resulting from disease processes affecting the integrity of the tricuspid valve leaflets and/or valve apparatus, such as in rheumatic heart disease, tricuspid valve prolapse or endocarditis. In contrast, functional (secondary or non-structural) TR refers to regurgitation occurring in the absence of significant structural disease of the tricuspid valve and/or apparatus. Functional TR occurs in approximately 80% of cases of significant TR [2], resulting from annular dilation and right ventricular enlargement, which is often secondary to left heart failure from myocardial or valvular causes, right ventricular volume and pressure overload, and dilation of cardiac chambers. Significant TR may be clinically silent for a prolonged period, during which time progressive right ventricle (RV) dilatation and dysfunction may develop, similar to changes that can occur with asymptomatic mitral regurgitation (MR) and its' effect on LV function.

[figure not shown]

Figure 1: Dilation of the Tricuspid Annulus – Dreyfus et al.[3]

Tricuspid regurgitation is a common echocardiographic finding that is often considered benign unless associated with significant pulmonary hypertension or RV or LV dysfunction. It has been shown that increasing TR severity is associated with worse survival regardless of LVEF or pulmonary artery pressure [1]. Severe TR is associated with a poor prognosis, independent of age, biventricular systolic function, RV size, and IVC dilation [1].

Figure 2: Kaplan-Meier survival curves for all patients with tricuspid regurgitation (TR). [1]

1.2 ALTERNATIVE TREATMENT/THERAPIES

[figure not shown]
1.2.1 SURGICAL TRICUSPID VALVE INTERVENTION

The decision to treat TR has been controversial over the years, but has recently become recommended in symptomatic patients and in some cases asymptomatic patients as

prophylactic treatment at the time of MR surgery [4]. The decision as to whether repair or replacement is recommended is demonstrated in the diagram below.

Figure 3: 2014 AHA/ACC Indications for Tricuspid Surgery [2]

Several techniques are available to correct functional tricuspid regurgitation. These include the stitch annuloplasty, such as semicircular (classical De Vega repair) or simple lateral annuloplasty (Kay), novel techniques such as edge-to-edge or clover technique and suture bicuspidization technique, use of flexible and rigid prosthetic rings or 3D rings, flexible prosthetic bands, and use of artificial chordae with polytetrafluoroethylene sutures for anterior and septal tricuspid leaflet pathology. Whereas the short-term outcomes of these techniques are satisfactory, the majority are limited in the mid- and long term by unacceptably high rates of residual and/or recurrent regurgitation [5].

While repair, specifically annuloplasty is considered the procedure of choice, if repair is not feasible or unsuccessful, replacement may be considered [6]. For replacement both bioprosthetic as well as mechanical valves provide viable options.

1.2.2 MEDICAL THERAPY

TR patients may be managed with diuretics for symptoms and only considered for surgery after advanced RV dysfunction, liver dysfunction or cirrhosis have developed. Additionally, medical therapies may be used to reduce elevated pulmonary artery pressures and/or pulmonary resistance [2].

For the patient population that would benefit from surgical intervention, but are characterized as high-risk or non-surgical, medical management is likely to only provide temporary symptom relief. The lack of benefit from medical therapies has prompted the search for alternative repair or replacement therapies.

1.2.3 PERCUTANEOUS TRICUSPID VALVE REPAIR

Percutaneous tricuspid valve repair therapies have considerable interest due to the minimally invasive nature of the procedures, particularly since surgery in functional patients is only indicated when they are undergoing concomitant valve surgery [2, 7].

Percutaneous devices are being investigated which mimic surgical repair techniques. These devices are targeted for patients which are at high operative risk for surgery. These devices aim to approximate the leaflets by anchoring in the annulus and pulling the anterior leaflet towards the posterior leaflet, simulating a bicuspidization. Another emerging technology is a device which uses pledgets in the annulus to reduce the size of the annulus.

1.2.4 TRANSCATHETER TRICUSPID VALVE REPLACEMENT

Transcatheter valve replacement with the Edwards Sapien or Medtronic Melody valve has been described in the published literature on only single case studies or limited retrospective clinical series but primarily for valve-in-valve patients or patients with rheumatic disease. This is not the patient population that the Edwards FORMA Tricuspid Transcatheter Repair system is intended for as the Edwards' device is intended for functional tricuspid regurgitation.

Additionally, percutaneous bicaval valve implantation has been used to treat tricuspid regurgitation by placing a valve in both the inferior vena cava and the superior vena cava. While this does not directly correct the TR it prevents back flow beyond the right atrium with the goal of reducing symptoms, normalizing liver function, and improving physical capacity.

1.3 IN-HOSPITAL/30-DAY MORTALITY

The most prevalent treatment options for tricuspid regurgitation are surgical repair or replacement. Typically, these procedures are done in conjunction with other cardiac surgical procedures (AVR, MVR, CABG,) while interventions performed in an isolated tricuspid regurgitation setting are quite rare. When performed, there are multiple factors that determine the success of the surgical intervention. The literature suggest that the most successful surgical interventions occur when tricuspid repair or replacement is performed as an elective procedure in conjunction with other cardiac procedures in a patient population that has a modest history of prior cardiac surgery. For example, McCarthy et al [8], reported an 8% in-hospital mortality when a large patient population with functional tricuspid regurgitation was treated using an annuloplasty approach. This

patient population will most likely represent a lower risk population than what is proposed in the SPACER Trial due to their more favorable disposition for cardiac surgery. An additional observation that cannot be overlooked, is the mortality rate in patients requiring reoperation. This article reports an alarming in-hospital mortality rate for reoperation patients of 37%. This is not an uncommon finding as Bernal et al [9] reported a 35% in-hospital mortality rate for a similar population of reoperation patients.

Ratnatunga et al [10] reported on a large patient population and concluded that for patients undergoing tricuspid regurgitation repair “a high mortality rate is universal.” Specifically, they suggest an approximate 18% operative mortality rate in a patient population with a higher NYHA functional classification distribution than McCarthy [8] as well as a blend of isolated TR surgery and TR surgery in conjunction with other cardiac surgery procedures. These results are in line with what Filsoufi et. al. [11] and Moraca et. al. [12] reported for a similar patient population (22% and 18%, respectively). In summary, operative mortality (also described as 30-day or in-hospital mortality) is very high for patients undergoing tricuspid regurgitation intervention. The most significant predictors of a higher mortality rate are previous cardiac surgery, previous tricuspid intervention and high New York Heart Association Classification (NYHA) functional class, all of which are inclusion criteria for the SPACER Trial. This literature review, summarized in Table 1 below, was the basis for determining the performance goal to which the safety of the Edwards Transcatheter Tricuspid Repair Device will be compared (reference Section 13 of this investigational plan).

Table 1 – Tricuspid Regurgitation Mortality Literature Review

Author	In-Hospital Mortality Rate	Patient Population (N)	Reference
McCarthy	6% (8% Hospital), 37% Re-Op	790	J Thorac Cardiovasc Surg 2004; 127:674-85
Bernal	35.1% Re-Op	74	J Thorac Cardiovasc Surg 2005;130:498-503
Ratnatunga	15.6%-18.8%	425	Ann Thorac Surg 1998; 66:1940-7
Filsoufi	22%	81	Ann Thorac Surg 2005; 80:845-50
Moraca	18% (repair), 13% (replacement)	136	Ann Thorac Surg 2009; 87:83-9
Pfannmuller	14.6%	82	J Thorac Cardiovasc Surg 2013; 146:841-7

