7.2 INCLUSION CRITERIA

The Investigator has the responsibility of screening potential subjects to determine if the patients meet all the inclusion criteria. The following are requirements for entry into the study:

1. Signed and dated EC approved study consent form prior to study related procedures
2. Eighteen years of age or older
3. Clinically significant, symptomatic (NYHA Functional Class II or greater), tricuspid regurgitation (Stage D per 2014 AHA/ACC guidelines) requiring tricuspid valve repair or replacement as assessed by the Heart Team
4. Functional tricuspid regurgitation (e.g., EROA \geq 0.4 cm² or equivalent guideline directed value) as the primary etiology
5. NYHA Functional Class II or greater or signs of persistent right heart failure despite optimal medical therapy
6. Determined by the 'HEART Team' (a minimum of one Cardiologist, and one Cardiac Surgeon) to be at high surgical risk for tricuspid valve repair or replacement and the benefit-risk analysis supports utilization of the investigational device
7. Willing to attend study follow-up assessments for up to 3 years

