18. Previously treated tricuspid valve which included implantation of a bioprosthetic valve or mechanical valve
19. Known hypersensitivity to cobalt chromium, nitinol or titanium
20. Known hypersensitivity to anticoagulation therapy or contrast agent, which cannot be adequately medicated

21. Patient is a current intravenous drug user
22. Female of child-bearing potential is pregnant or lactating
23. Patient is currently participating or has participated in another investigational drug or device clinical study within 30 days of study screening activity
24. Patient requires emergent/emergency treatment for tricuspid insufficiency
25. Patient is under guardianship

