² If a pre-existing CT within 6 months of the scheduled implant procedure captures all the required anatomy for necessary measurements and the anatomy has not changed, the baseline CT can be waived and is not required to be repeated.

tricuspid valve and sub-valvular structures/anatomy, right atrium and right ventricle. Analysis will be conducted by the Investigator and Sponsor/designee to certify the subject is eligible for the study.

9. Invasive Hemodynamic Monitoring/Right Heart Catheterization (within 45 days of scheduled implant procedure) that includes, but is not limited to, right atrial pressure (RAP) and pulmonary artery pressure (PAP) measurements.³

Baseline evaluation data to be collected will include but is not limited to the information listed in the following table.

Table 4 - Baseline Evaluation

General Information	Clinical Information	Laboratory Measurements

 • Inclusion/exclusion evaluation • Informed consent • Age • Gender • Height • Weight 	
 • Heart Team determination • Medical history (e.g., EuroSCORE) /prior cardiovascular interventions / surgeries • Vital signs (Blood pressure, heart rate) • Concomitant Medication • NYHA classification¹ • Echocardiographic measurements (TTE & TEE), tricuspid regurgitation & heart function • Computed Tomography (CT) • Invasive Hemodynamic Monitoring/Right Heart Catheterization including pressure measurements • ECG results • Six minute walk test (pre & post walk data & results) • KCCQ & SF-12 questionnaires 	
Within 30 days of procedure:
 
 • Date of blood draw • Troponin² and/or CK-MB² 
Within ≤ 2 weeks of procedure:
 
 • Date of blood draw • BNP • WBC • RBC • Hematocrit • Hemoglobin • Platelets • ALT/SGPT • AST/SGOT • Bilirubin • LDH • Sodium & potassium • Urea 
Within ≤ 48 hours of procedure:
 
 • eGFR³ • PTT/aPTT or PT/INR • βHCG, if applicable⁴

1. Classification of < NYHA II is an exclusion from study participation
2. MI within 30 days of the scheduled implant procedure is an exclusion from study participation
3. eGFR result of < 25 is an exclusion from study participation
4. A positive result is an exclusion from study participation

³ If the screening echo confirms the PAP meets the study criteria, the right heart catheterization/hemodynamic assessment at the baseline evaluation may be waived.

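### Do the misdescribed inclusion criteria in Section 1.3, and its merging of in-hospital with 30-day mortality, undermine the 18% performance goal?

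*Protocol*

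**What the plan says.** Protocol Section 1.3 reviews surgical mortality and names the strongest predictors of death: earlier heart operations, "previous tricuspid intervention and high New York Heart Association Classification (NYHA) functional class, all of which are inclusion criteria for the SPACER Trial". It then makes the literature summary in Table 1 the basis for the performance goal.

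Section 7.2 sets the actual entry rules. Criterion 3 asks for "Clinically significant, symptomatic (NYHA Functional Class II or greater), tricuspid regurgitation" at Stage D, and criterion 6 asks that the Heart Team judge the patient "to be at high surgical risk for tricuspid valve repair or replacement and the benefit-risk analysis supports utilization of the investigational device". Table 4, footnote 1, repeats the NYHA threshold: "Classification of < NYHA II is an exclusion from study participation". No criterion asks for earlier cardiac surgery or an earlier tricuspid procedure. Exclusion 18 in Section 7.3 in fact bars one kind of earlier tricuspid procedure: "Previously treated tricuspid valve which included implantation of a bioprosthetic valve or mechanical valve".

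On the outcome, Section 1.3 concludes that "operative mortality (also described as 30-day or in-hospital mortality) is very high", and the rate column of Table 1 is headed "In-Hospital Mortality Rate". The primary endpoint (Protocol 13.4, SAP 3.2) is all-cause death by day 30 in the As Treated cohort. The test passes if the one-sided 95% Kaplan-Meier/Greenwood upper limit is below 18%. The other planned mortality estimates are at 6 months and 1, 2 and 3 years (Protocol 13.5, SAP 3.3).

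**The concern.** In a single-arm trial the performance goal is the whole comparison. If its written justification describes sicker patients than the trial admits, the goal may be too lenient. Prior surgery and prior tricuspid intervention are said to be the main drivers of operative death, so claiming that every subject has them overstates the match with the surgical series.

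The outcome definition raises a similar doubt. In-hospital mortality counts deaths after day 30 during a long index stay and omits deaths after discharge but before day 30. Table 1 gives one large annuloplasty series two figures, 6% and 8%, the second labelled as hospital mortality, so the choice of definition can move a rate. The primary test turns on a single death near the threshold, and nothing in the visible plan shows whether a pass would also hold under the other definition.

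**Working it through.** **1. The plan's own figure.** Inputs from Protocol 13.1: goal 18%, assumed true rate 7.5%, n = 63, level 0.05; Section 13.4 makes it one-sided. The exact binomial test rejects at 6 or fewer deaths: P(X ≤ 6 | 63, 0.18) = 0.0487 and P(X ≤ 6 | 63, 0.075) = 0.808. The stated 80% power reproduces. Neither half of the concern alters an input.

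**2. Section 1.3 against Sections 7.2 and 7.3.**

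| Predictor in 1.3 | Required by 7.2? | Restricted by 7.3? |
|---|---|---|
| Previous cardiac surgery | No | Any therapeutic invasive cardiac procedure in the 30 days before implant (exclusion 4) |
| Previous tricuspid intervention | No | Prior bioprosthetic or mechanical tricuspid valve (exclusion 18) |
| High NYHA class | Class II or greater | Below class II (Table 4, footnote 1) |

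So 1.3 is wrong for two predictors and loose for the third.

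**3. Does the 18% depend on the wrong sentence?** The re-operation rates in Table 1 are 37% and 35.1%. Had the goal been built on a reoperative population, it would be expected near those figures. Apart from them and the annuloplasty series (6%, 8%), Table 1 runs from 13% to 22%: 13%, 14.6%, 15.6% to 18.8%, 18% and 22%. The goal lies inside that range. Section 1.3 ties it to a series chosen for its NYHA mix: "they suggest an approximate 18% operative mortality rate in a patient population with a higher NYHA functional classification distribution".

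**4. How close is the decision to one death?** Without censoring, p = d/n, S = 1 − p and se = √(pS/n). The plan names no transformation, so both usual limits are shown:
- untransformed: p + 1.645·se
- log-log: 1 − S^exp(1.645·se/(S·|ln S|))

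| Deaths of 63 | Untransformed limit | Log-log limit |
|---|---|---|
| 6 | 15.6% | 17.8% (last pass) |
| 7 | 17.6% (last pass) | 19.7% |
| 8 | 19.6% | 21.6% |

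At a true rate of 7.5%, the chance of landing exactly on the last passing count is P(X = 7) = 9.4% (untransformed) or P(X = 6) = 14.2% (log-log).

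**5. What would a combined count do?** Count a death if it occurs by day 30 or before index discharge. Let q be the probability that a subject dies in the index stay after day 30. The documents give no value, so q is assumed. With c the last passing count, X ~ Binomial(63, 0.075) and L late deaths, where L given X is Binomial(63 − X, q/0.925), the chance that the primary passes and the combined count fails is P(X ≤ c and X + L > c).

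| Assumed q | Expected late deaths (63q) | c = 7, untransformed | c = 6, log-log |
|---|---|---|---|
| 0.1% | 0.06 | 0.6% | 0.9% |
| 0.5% | 0.32 | 3.1% | 4.6% |
| 1% | 0.63 | 6.6% | 9.5% |
| 2% | 1.26 | 14.9% | 19.9% |

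At q = 0 the two analyses are identical. The larger entries need q of 1% to 2%, which is 13% to 27% of the assumed 30-day rate (1/7.5 and 2/7.5). Nothing in the documents supports a value that high or rules it out.

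**The case for a change.** The best case for acting is that the documents are meant for regulatory use (Protocol Section 2). Anyone checking the goal will set 1.3 beside 7.2 and find the contradiction, and Heart Team judgement may bring in reoperative patients but guarantees none. If the right benchmark were one of the lower Table 1 rates, the 18% goal would be too easy: a device with true mortality of 13%, 14.6% or 15.6% would meet the exact 18% rule with probability 27.3%, 16.8% or 12.0%. A combined-definition analysis specified in advance would cost a paragraph and prevent an argument after a narrow pass.

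The contradiction stands. The rest does not lead to a change. Those probabilities show what a wrong goal would cost; they do not show that this goal is wrong, and correcting a clause about eligibility would not move it. A corrected clause also needs care: calling prior procedures simply permitted would overlook exclusions 4 and 18.

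The combined count can only equal or exceed the 30-day count. A pass would be reassuring. A failure could not be read, because the count is larger than under either definition alone. It is also not established that 18% is an in-hospital figure: the prose of 1.3 calls the 18% series operative mortality and attaches in-hospital to the 8%, 37% and 35% figures. Discharge in Section 8.6.3 is from the hospital or unit, so even the combined definition would need further wording.

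The information is not lost. Deaths are listed for all enrolled subjects (Protocol 13.3, SAP 2.4), discharge dates are collected (Table 7) and index length of stay is summarised (SAP 4.1.3). With about 63 subjects, late index-stay deaths can largely be checked from the listings.

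**Conclusion.** No change to the plan is needed. The inclusion-criteria clause in Section 1.3 is a drafting error in background text. It affects no eligibility rule, sample size, test or result, and the 18% goal is consistent with the general series quoted beside it. The clause can be aligned with Sections 7.2 and 7.3 if that section is opened for another reason.

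The merging of mortality definitions is a fair simplification given what the documents show. They do not say which definition underlies 18% or which way the two differ. The possible effect on the decision runs from nil, with no late index-stay deaths, to 19.9% at an assumed late death rate of 2% under the log-log limit. These figures assume 63 subjects, no censoring, true 30-day mortality of 7.5% and the listed late-death rates. An analyst who wants the comparison can give the combined count as a descriptive line in the report without amending anything.

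This conclusion does not settle whether 18% is the best choice from Table 1. It says only that these two points do not show it to be wrong.
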